APPENDIX E. SAMPLE FOOD CRAVING INVENTORY (FCI)

Food Craving Inventory-II

For each of the foods listed below (Items 1 – 28), please mark the appropriate bubble using the following scale.

A craving is defined as an intense desire to consume a particular food (or food type) that is difficult to resist.

Over the past month, how often have you experienced a craving for the food?

	Never	Rarely (once or twice)	Sometimes	Often	Always/ Almost every day
1. Cake					
2. Pizza					
3. Fried Chicken					
4. Gravy					
5. Sandwich Bread					
6. Sausage					
7. French fries					
8. Cinnamon Rolls					
9. Rice					
10. Hot dog					
11. Hamburger					
12. Biscuits					
13. Ice cream					
14. Pasta					
15. Fried fish					
16. Cookies					
17. Chocolate					
18. Pancakes or waffles					
19. Corn bread					
20. Chips					
21. Rolls					
22. Cereal					
23. Donuts					
24. Candy					
25. Brownies					
26. Bacon					
27. Steak					
28. Baked potato					

**APPENDIX F. SAMPLE IMPACT OF WEIGHT ON QUALITY OF LIFE-
LITE (IWQOL-LITE) QUESTIONNAIRE**

Impact of Weight on Quality of Life Questionnaire—Lite Version (IWQOL-Lite)

Please answer the following statements by circling the number that best applies to you in the past week. Be as open as possible. There are no right or wrong answers.

Physical Function		ALWAYS TRUE	USUALLY TRUE	SOMETIMES TRUE	RARELY TRUE	NEVER TRUE
1.	Because of my weight I have trouble picking up objects.	5	4	3	2	1
2.	Because of my weight I have trouble tying my shoes.	5	4	3	2	1
3.	Because of my weight I have difficulty getting up from chairs.	5	4	3	2	1
4.	Because of my weight I have trouble using stairs.	5	4	3	2	1
5.	Because of my weight I have difficulty putting on or taking off my clothing.	5	4	3	2	1
6.	Because of my weight I have trouble with mobility.	5	4	3	2	1
7.	Because of my weight I have trouble crossing my legs.	5	4	3	2	1
8.	I feel short of breath with only mild exertion.	5	4	3	2	1
9.	I am troubled by painful or stiff joints.	5	4	3	2	1
10.	My ankles and lower legs are swollen at the end of the day.	5	4	3	2	1
11.	I am worried about my health.	5	4	3	2	1
Self-esteem		ALWAYS TRUE	USUALLY TRUE	SOMETIMES TRUE	RARELY TRUE	NEVER TRUE
1.	Because of my weight I am self-conscious.	5	4	3	2	1
2.	Because of my weight my self-esteem is not what it could be.	5	4	3	2	1
3.	Because of my weight I feel unsure of myself.	5	4	3	2	1
4.	Because of my weight I don't like myself.	5	4	3	2	1
5.	Because of my weight I am afraid of being rejected.	5	4	3	2	1
6.	Because of my weight I avoid looking in mirrors or seeing myself in photographs.	5	4	3	2	1
7.	Because of my weight I am embarrassed to be seen in public places.	5	4	3	2	1

Sexual Life		ALWAYS TRUE	USUALLY TRUE	SOMETIMES TRUE	RARELY TRUE	NEVER TRUE
1.	Because of my weight I do not enjoy sexual activity.	5	4	3	2	1
2.	Because of my weight I have little or no sexual desire.	5	4	3	2	1
3.	Because of my weight I have difficulty with sexual performance.	5	4	3	2	1
4.	Because of my weight I avoid sexual encounters whenever possible.	5	4	3	2	1

Public Distress		ALWAYS TRUE	USUALLY TRUE	SOMETIMES TRUE	RARELY TRUE	NEVER TRUE
1.	Because of my weight I experience ridicule, teasing, or unwanted attention.	5	4	3	2	1
2.	Because of my weight I worry about fitting into seats in public places (e.g. theaters, restaurants, cars, or airplanes).	5	4	3	2	1
3.	Because of my weight I worry about fitting through aisles or turnstiles.	5	4	3	2	1
4.	Because of my weight I worry about finding chairs that are strong enough to hold my weight.	5	4	3	2	1
5.	Because of my weight I experience discrimination by others.	5	4	3	2	1
Work (Note: For homemakers and retirees, answer with respect to your daily activities.)		ALWAYS TRUE	USUALLY TRUE	SOMETIMES TRUE	RARELY TRUE	NEVER TRUE
1.	Because of my weight I have trouble getting things accomplished or meeting my responsibilities.	5	4	3	2	1
2.	Because of my weight I am less productive than I could be.	5	4	3	2	1
3.	Because of my weight I don't receive appropriate raises, promotions or recognition at work.	5	4	3	2	1
4.	Because of my weight I am afraid to go on job interviews.	5	4	3	2	1

APPENDIX G. PARTIAL LIST OF PROHIBITED CYTOCHROME P450 (CYP) 3A4 INDUCERS AND MODERATE-TO-STRONG INHIBITORS

Partial List of Cytochrome P450 3A4 (CYP3A4) Inhibitors and Inducers (This is not an exhaustive list.)

Moderate to Strong CYP3A4 inhibitors:

Amprenavir
Aprepitant
Atazanavir
Boceprevir
Ciprofloxacin
Clarithromycin
Conivaptan
Crizotinib
Darunavir/ ritonavir
Diltiazem
Erythromycin
Fosamprenavir
Fluconazole
Imatinib
Indinavir
Itraconazole
Ketoconazole
Lopinavir/ ritonavir
Nefazodone
Nelfinavir
Posaconazole
Ritonavir
Saquinavir
Telaprenavir
Telithromycin
Troleandomycin

Verapamil

Voriconazole

Partial List of Moderate to Strong CYP3A4 inducers:

Bosentan

Carbamazepine

Efavirenz

Etravirine

Modafinil

Nafcillin

Nevirapine

Phenobarbital

Phenytoin

Rifampin

Rifabutin

St. John's Wort

1 INTRODUCTION

This statistical analysis plan (SAP) describes the statistical methods to be used for analyses and data presentation for reporting efficacy and safety results for study ALK3831-302. This document has been prepared based on Alkermes ALK3831-302 Study Protocol Amendment 2 (dated 16 February 2014) [1].

1.1 STUDY OBJECTIVES

The objectives of this study are to evaluate 3 doses of samidorphan co-administered with olanzapine (ALKS 3831) in subjects with schizophrenia to (1) evaluate ALKS 3831 as a treatment for schizophrenia, (2) assess the safety and tolerability of ALKS 3831, and (3) characterize the impact of samidorphan component of ALKS 3831 on weight and other metabolic factors.

1.2 SUMMARY OF THE STUDY DESIGN

This is a Phase 2, randomized, placebo-controlled multicenter study that is divided into 2 parts: Part A and Part B.

Part A will begin with screening followed by a 1-week olanzapine lead-in period where subjects will receive olanzapine daily and a 12-week double-blind, placebo-controlled treatment period where subjects will receive samidorphan or placebo (in addition to the olanzapine prescribed on Study Day 1) daily. Olanzapine dosing will be selected and titrated by the investigator based upon individual subject needs and consistent with current clinical practice. Subjects will be randomized in a 1:1:1:1 ratio to receive either samidorphan (5, 10, or 20 mg) or placebo.

Part B will include an additional 12-week treatment period where all subjects will receive active olanzapine + samidorphan (ie, ALKS 3831). Subjects randomized to samidorphan during Part A will continue receiving the same dose of samidorphan during Part B. Subjects randomized to placebo during Part A will receive the highest dose of samidorphan during Part B. Dose level during Part B will be double-blind. For all subjects, samidorphan dosing will stop at the end of Part B, but olanzapine dosing will continue uninterrupted through a 4-week follow-up period, which includes 2 safety visits.

This study will use an independent Data Safety Monitoring Board (DSMB) to monitor subject safety data. After at least one week of safety data has been collected for 40 randomized subjects, the DSMB will review the accumulated safety data for all subjects. After at least one week of safety data has been collected for 150 randomized subjects, the DSMB will review the accumulated safety data for all subjects. Additional reviews of the data may occur at the discretion of the DSMB. Complete details of the data review procedures of the DSMB are available in the DSMB charter.

This is the first study of ALKS 3831 in a population of adults with schizophrenia. Subjects will be monitored in an inpatient setting for 2 nights following randomization (Visit 3) and during the transition from Part A to Part B (Visit 13). These are the two periods where samidorphan treatment may be initiated. Subjects will be monitored in an inpatient setting whether or not samidorphan treatment is being initiated in order to maintain double-blind dosing and a consistent subject experience consistent across treatment groups.

2 SAMPLE SIZE CONSIDERATIONS

Sample size calculations are based on the primary endpoint of absolute change in PANSS total score. These calculations assume an equivalence margin of 10 points, a standard deviation of 20 points, and a true difference of 0 points. With these assumptions, 280 randomized subjects provide 95% power to demonstrate equivalence on the primary endpoint (absolute PANSS total score change from randomization to the end of Part A) with a 2-sided test at an alpha level of 0.05. These 280 subjects represent 70 subjects for each treatment arm (ALKS 3831 5 mg, ALKS 3831 10 mg, ALKS 3831 20 mg, and placebo) in a 1:1:1:1 ratio. For the primary analysis, subjects in the 3 ALKS 3831 treatment groups will be pooled for comparison with placebo. If this analysis shows equivalence, follow-up analyses on individual dose levels will be performed. Assuming a 20% discontinuation rate prior to randomization, an estimated 350 subjects will be enrolled in this study.

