The secondary endpoint, percent change in weight from randomization to the end of Part A, will be evaluated by treatment group using an MMRM approach similar to that of the primary endpoint. However, this will be a superiority analysis. Each treatment group will be compared to the placebo

group with a 2-sided hypothesis test to test for superiority at an alpha level of 0.05. The secondary efficacy analysis will also be conducted in the FAS 1 population. More details about this analysis will be provided in the SAP.

Analysis of other secondary endpoints and additional endpoints will include inferential analyses and descriptive analyses by visit (mean, standard deviation, median, minimum, and maximum for continuous variables and number and percent for categorical variables), as appropriate.

Analyses for the primary and secondary endpoints will be repeated in the FAS 2 population as sensitivity analyses when applicable. Additional details regarding these analyses will be provided in the SAP.

Sample size considerations

Sample size calculations are based on the primary endpoint of absolute change in PANSS total score. These calculations assume an equivalence margin of 10 points, a standard deviation of 20 points, and a true difference of 0 points. With these assumptions, 280 randomized subjects provide 95% power to detect equivalence on the primary endpoint (absolute PANSS total score change from randomization to the end of Part A) with a 2-sided test at an alpha level of 0.05. These 280 subjects represent 70 subjects for each treatment arm (ALKS 3831 5 mg, ALKS 3831 10 mg, ALKS 3831 20 mg, and placebo) in a 1:1:1:1 ratio. For the primary analysis, subjects in the 3 ALKS 3831 treatment groups will be pooled for comparison with placebo. If this analysis shows equivalence, follow-up analyses on individual dose levels will be performed. Assuming a 20% discontinuation rate prior to randomization, an estimated 350 subjects will be enrolled in this study.

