7.4. Replacement of Subjects

Subjects who withdraw from the study after randomization will not be replaced.

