14. STATISTICS

14.1. Sample Size Considerations

Sample size calculations are based on the primary endpoint of absolute change in PANSS total score. These calculations assume an equivalence margin of 10 points, a standard deviation of 20 points, and a true difference of 0 points. With these assumptions, 280 randomized subjects provide 95% power to demonstrate equivalence on the primary endpoint (absolute PANSS total score change from randomization to the end of Part A) with a 2-sided test at an alpha level of 0.05. These 280 subjects represent 70 subjects for each treatment arm (ALKS 3831 5 mg, ALKS 3831 10 mg, ALKS 3831 20 mg, and placebo) in a 1:1:1:1 ratio. For the primary analysis, subjects in the 3 ALKS 3831 treatment groups will be pooled for comparison with placebo. If this analysis shows equivalence, follow-up analyses on individual dose levels will be performed. Assuming a 20% discontinuation rate prior to randomization, an estimated 350 subjects will be enrolled in this study.

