3.6 EFFICACY ANALYSIS

3.6.1 Change in PANSS total Score

The primary endpoint is the change in PANSS total score from randomization to Day 92 and will be evaluated by treatment group (ALKS 3831 pooled vs. the placebo group [olanzapine alone]) using a 2-sided mixed-model for repeated measures (MMRM) to test for equivalence at an alpha level of 0.05. The primary analysis will be conducted in the FAS 1 population.

The null hypothesis is that the PANSS total score change from randomization to Day 92 of ALKS 3831 treatment group will be different to that of the placebo group [olanzapine alone]. The bound of the 2-sided 95% CIs of the difference between the changes of ALKS 3831 – Placebo [olanzapine alone] will be outside the equivalence interval of -10 and 10.

If this analysis shows equivalence, similar analyses on individual dose levels will be performed.

Change in PANSS total score from baseline to Day 92 will be analyzed using MMRM model. The MMRM model will include variables for weight change strata in the olanzapine lead-in period, treatment group, visit, and treatment group-by-visit interaction term as categorical fixed effect, baseline value will be included as a covariate. An AR(1) covariance structure will be

applied for the MMRM. The Kenward-Roger approximation [2] will be used to adjust the denominator degree of freedom. The analysis will be performed on all observed post-randomization scores without imputation of missing data.

A sample of SAS implementation code for analyzing change from randomization to Day 92 using an MMRM is given below.

```
proc mixed data=datain;  
class strata usubjid trt visit;  
  model change = strata trt visit trt*visit base  
    / DDFM=KENWARDROGER;  
repeated visit/ type=AR(1) subject=usubjid;  
lsmeans trt*visit / diff cl;  
run;
```

The least squares (LS) mean, standard error (SE), and LS mean difference between pooled ALKS 3831 treatment group and placebo [olanzapine alone], as well as between each ALKS 3831 treatment group and the placebo [olanzapine alone] at Day 92, along with the 95% CI, will be summarized.

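### The stated 95% power does not match the SAP's 95% CI equivalence rule, under which 280 subjects give about 90%, and less after dropout

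*SAP*

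**What the plan says.** The sample size text is essentially the same in three places. On the inputs, SAP section 2 states: "These calculations assume an equivalence margin of 10 points, a standard deviation of 20 points, and a true difference of 0 points". It then gives the result, "With these assumptions, 280 randomized subjects provide 95% power to demonstrate equivalence on the primary endpoint", and describes the test as "with a 2-sided test at an alpha level of 0.05". On the arm sizes it says "These 280 subjects represent 70 subjects for each treatment arm", and the three active arms are pooled for the primary comparison. Protocol 14.1 repeats the claim ("280 randomized subjects provide 95% power to demonstrate equivalence on the primary endpoint"), as does the protocol synopsis ("280 randomized subjects provide 95% power to detect equivalence on the primary endpoint").

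The decision rule is in SAP 3.6.1. It frames the null hypothesis through "The bound of the 2-sided 95% CIs of the difference" in change scores falling outside -10 to 10, so equivalence requires the whole 95% CI to lie inside that interval. SAP 3.1 and protocol 14.2 set all tests and CIs at 2-sided 0.05 unless stated otherwise. Neither document mentions a 90% CI or two one-sided tests at 5%.

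The only attrition allowed for is 20% before randomization, which takes 350 enrolled to 280 randomized. Protocol 7.4 adds: "Subjects who withdraw from the study after randomization will not be replaced".

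**The concern.** In an equivalence test both confidence bounds must clear the margin, so the CI level fixes the error rate on each side: a 95% CI spends 0.025 per side and a 90% CI spends 0.05. A power figure is meaningful only under the rule that will actually be applied. Here the sample size section and the decision rule appear to use different rates per side.

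This is the primary endpoint. A reader of the plan would believe that a truly equivalent product has a 1 in 20 chance of failing, when the written rule gives it roughly a 1 in 10 chance before any subject drops out. The individual-dose analyses are performed only if the pooled test succeeds, so they inherit that risk. If the inconsistency were left until the data are unblinded, the choice between a 90% and a 95% CI could itself decide the primary result.

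**Working it through.** **Inputs.** Margin 10, SD 20, true difference 0, 70 per arm and pooling to 210 versus 70 (SAP section 2). The 2-sided 95% CI must lie inside -10 to 10 (SAP 3.6.1).

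**Standard error.** SE = 20 × √(1/210 + 1/70) = 2.760, so margin/SE = 10/2.760 = 3.623.

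**Formula.** With a true difference of 0, power = 2Φ(margin/SE − z) − 1, where z is the critical value for each side.

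**Reproducing the stated 95%.**
- 90% CI (0.05 per side, z = 1.645): 2Φ(1.978) − 1 = 95.2%; 95.1% with t. On this basis 280 is the smallest total, in steps of four, that reaches 95% (t version).
- One bound only at 0.025 (non-inferiority, z = 1.960): Φ(1.663) = 95.2%.

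**Under the rule in SAP 3.6.1.**
- 95% CI (0.025 per side, z = 1.960): 2Φ(1.663) − 1 = 90.4%; 90.1% with t.
- Probability of missing equivalence when the arms are identical: 100 − 90.4 = 9.6%, against 5% implied.

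**After post-randomization loss.** The documents give no rate, so 10% to 30% is an assumed range. These values take equal loss in all arms and no recovery of information by the MMRM.

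| Loss | Pooled vs placebo | SE | Power, 95% CI rule |
|---|---|---|---|
| 0% | 210 vs 70 | 2.760 | 90.4% |
| 10% | 189 vs 63 | 2.910 | 86.0% |
| 20% | 168 vs 56 | 3.086 | 80.0% |
| 30% | 147 vs 49 | 3.299 | 71.6% |

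**One dose against placebo (70 vs 70, full retention).** SE = 20 × √(2/70) = 3.381 and margin/SE = 2.958, so power = 2Φ(0.998) − 1 = 68.2%. All three doses passing, allowing for the shared placebo arm: about 37% by simulation.

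**N for 95% under the 95% CI rule.** 82 per arm (328 evaluable) by the normal formula, 83 per arm (332) with t, before any dropout allowance.

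**The case against.** The strongest reply is that nothing was miscalculated. Two one-sided tests at 5% is a recognised convention, it gives 95.2%, and 280 fits it exactly. Protocol 14.4 speaks only of testing equivalence at an alpha level of 0.05, which taken alone could mean 5% per side, so the error might lie in the CI level of SAP 3.6.1. This stands as an explanation of where 95% may have come from, and it means there are two ways to reconcile the text. It does not rescue the figure, because the only decision rule written down uses the 95% CI.

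Second, the dropout figures rest on assumed rates and ignore what the MMRM recovers from earlier visits. That is correct. As an illustration, take AR(1) correlation across the five post-baseline PANSS visits in Part A and 20% loss spread evenly over visits. Power is then about 81% at a correlation of 0.5 and 87% at 0.9 (both correlations assumed). So 80% is the pessimistic end for that loss rate. The 90.4% figure needs no dropout assumption.

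Third, baseline PANSS is a covariate, and if SD 20 is unadjusted, a residual SD of about 18.5 would restore 95%. The plan claims no such gain.

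Fourth, the 95% CI is the stricter rule, so false-positive control is not harmed, and no per-dose power was promised. Both points are fair: the shortfall is one of power only, and the per-dose figures are useful context on which the finding does not depend.

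**Conclusion.** The point holds. On the plan's own inputs and its own 95% CI rule, the primary comparison has about 90% power with all 280 subjects evaluable, not 95%. This rests only on margin 10, SD 20, true difference 0, a 210 versus 70 split and the decision rule in SAP 3.6.1. The further fall with dropout is certain in direction but not in size: about 86%, 80% or 72% at 10%, 20% or 30% loss if the MMRM recovers nothing, and somewhat higher if it does.

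The shortfall is moderate and does not threaten the validity of the test. It still has to be corrected, because the power claim and the decision rule for the primary endpoint cannot both stand as written.

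**What to change.** Keep the 95% CI rule and correct the power statement in the protocol synopsis, protocol 14.1 and SAP section 2:

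- State about 90% power for the pooled comparison, with equivalence declared when the 2-sided 95% CI lies within -10 to 10 and all 280 subjects evaluable.
- Add the power at the post-randomization dropout the sponsor expects, naming that rate and its basis. At 20% it would be about 80% with no MMRM recovery.
- Give the single-dose figure (about 68% at full retention) so that readers can judge the follow-up dose analyses. This is advisable but not essential to the correction.

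If the sponsor in fact intended two one-sided tests at 5%, the alternative is to name the 90% CI in SAP 3.6.1. That restores 95% at full retention, but it relaxes the written criterion and must be settled before unblinding.

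The recommended route costs wording in three places and a less favourable power figure. N does not change. Keeping 95% under the 95% CI rule would instead need about 328 to 332 evaluable subjects.

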3 DATA ANALYSIS

3.1 GENERAL STATISTICAL METHODOLOGY

In general, descriptive statistics: n, mean (SD), median, minimum, and maximum, for continuous variables and number and percentage of subjects in each category for categorical variables will be provided by treatment group for all variables.

All statistical tests and confidence intervals (CIs), unless stated otherwise, will be 2-sided and will be set at an alpha level of 0.05.

All Source data will be presented as subject data listings.

Body weight will be measured 3 times at every visit. The median weight will be used in summary tables or figures.

3.1.1 Baseline Definition

Baseline for Part A is defined as the last non-missing observation on or before the first dose of study drug following randomization at Visit 3 (Day 8).

Baseline for Part B is defined as the last non-missing observation on or before the date of the first dose of study drug at Visit 13 (Day 92).

